We will now work on implementing the intervention and assessing changes across interventions with regard to Aims 1-3 outcomes (screening, psychosocial facilitators, network effects). We plan on recruiting 150 Latina women to participate in the Intervention. 75 women will be recruited at The Resurrection Project and 75 women will be recruited from Centro Comunitario Juan Diego. No contact information on women who have participated in any previous focus groups or will we re-contact any woman who has already participated in a focus group for future trial. We will only invite new recruits for the intervention. We will be conducting educational classes and workshops at the two participating sites. The Intervention is broken down into 3 sessions at each site across 3 consecutive weeks. Each session will be held with 5-8 recruited participants. We will hold 5 – 9 sessions at each participating site for three consecutive weeks until we reach our target population of 150 Latina women. The variations in the implementation of Phase 3 Intervention will be the Workshops at each site. Besides each site conducting a Breast Cancer Education session at Session 1, TRP will conduct Communication and Volunteerism workshops at Session 1 and 2. Juan Diego will conduct Diet and Physical Activity workshops at Session 1 and 2. Our outcomes will be measured by Surveys assessed during Session 1, Session 3, and six months post-participation in workshops for 20-30 minutes. At the end of Phase 3, participants who have agreed to be contacted again will be contacted by study staff by phone and given the opportunity to learn about preliminary analyses. Participants will be offered information regarding preliminary analyses of the study. They will have the opportunity to decline learning about study results without any negative impact/costs to their relationships with the study sites or UIC. Script for these calls was submitted as part of Amendment #24.

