- For peer-referrals, women will be probed for perceived coercion, will be told that the study is voluntary, will be told that peers will receive compensation regardless of whether they choose to participate or not, and that the peer will not know about the extent to which women choose to participate (e.g., in screening or in intervention sessions).
- Women who call to inquire about the study will listed in a Call Log. We will utilize the call log to invite the women to participate in the interventions. [name] and UIC Staff (Appendix P) are bilingual to handle any calls from only Spanish and only English speaking subjects.
- Participants have the right to be removed from the research study at any point. This is a development study and therefore, no further information will be collected on the subject. The PI will be notify the participant that any information collected will remain confidential and any further contact by the research staff will cease.

For Phase 4, we will recruit approximately 20 individuals (10 related to empowerment and 10 related to education):

- Phase 3 participants will be told about the opportunity to recruit their family and friends through sharing flyers/coupons and/or providing [name] contact information for screening. Participants will have the opportunity to take recruitment flyers throughout the three intervention sessions. The number of flyers given to each participant will depend on the participant's interest in distribution and how many they want. The study staff will record the total number each person obtains as well as the respective codes. When recruiting family and friends, seed participants will provide individuals with flyers. How many flyers are distributed and to whom will depend on the seed participants' interests and actions after they take the flyers from study staff. When interested individuals call, they will be told not to provide information from the seed participants. Given this, there will be no record of which Phase 3 participant referred whom nor of which potential Phase 4 participants called, screened, and participated.
- Interested participants will call the PI, [name], or UIC staff [Appendix P], who will enter the name, address and phone number in a Call Log; screen individuals for eligibility; and obtain scheduling information.

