which women ultimately consent and participate in interventions. Study staff will have no contact information concerning the women who are reached by the peers, Centro Comunitario Juan Diego and The Resurrection Project, unless women contact study staff directly. Peers, Centro Comunitario Juan Diego and The Resurrection Project will not give any contact information to [name] and her team.

Interested women who have received the recruitment flyers, will contact UIC student/staff who will record women's contact information, screen them for eligibility, and obtain scheduling information for the Intervention sessions. We will ask each participant at time of recruitment/enrollment what language they prefer. Three 2-3 hour Workshop Sessions will then be scheduled for three consecutive weeks and held accordingly. For the Phase 3/Intervention, women will be informed that the sessions and workshops will be a "closed" group format. Once a woman agree to participate and enrolled in one of the 3 consecutive sessions, she cannot change or switch to another group's session.

With regard to interventions, once we have at least recruited 6-8 women per session, Centro Comunitario Juan Diego and The Resurrection Project will determine a date and time for use of conference room and fits within recruited women's schedules and begin the scheduling process. Once a date and time has been confirmed, UIC staff [Appendix P], will contact women two days prior to the session/s to remind them and reschedule, as needed. We will hold 5 – 9 sessions at each participating site for three consecutive weeks until we reach the targeted 150 Latina women.

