After the Session 3, participants will be asked to complete Survey 2 (T2) before leaving the site. Survey 2 will collect information related to volunteerism history, social interactions, breast cancer beliefs (cultural beliefs, perceived risks, norms and social interactions concerning breast cancer) and breast cancer screening since Survey 1.

All participants will receive a “book” of the PowerPoint slides as well as will have the option to use Promise Letters to encourage adherence to goals. This material will be kept at the participating sites with the Community Health Worker in a locked cabinet in a locked office. None of the materials will have personal identifying information; they will have the participant’s six digit random identification code. They will be collected by the UIC staff after Session 3.

UIC study staff and CHWs listed in Appendix P will begin conducting the Booster Calls (Follow-Up Calls) one month after the Educational Sessions. Everyone (UIC-based staff and CHWs) engaging in these calls will have access to the UIC/SPH R drive (R =Research), wherein all data will be stored. Each call will be approximately 10-20 minutes. The booster calls will be conducted every month for six months. These booster calls are intended to sustain successful behavior change and increase motivation.

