Six months after participation in Session 3, participants will be asked to complete Survey 3, which will take about 20-30 minutes. Survey 3 will be administered or in person at Centro Comunitario Juan Diego or The Resurrection Project sites. The reminder script has been modified to include scheduling calls, including for Survey 3 as well as the focus groups. Survey 3 will collect information related to information related to volunteerism history, social interactions, breast cancer beliefs (cultural beliefs, perceived risks, norms and social interactions concerning breast cancer) and breast cancer screening since Survey 1. For participants were in Cohort 1 (who completed participation before approved consent addendum), they will be contacted by phone up to 3 times with a script including consent addendum information to be given that information, wherein they can elect to be notified about future studies, if they are interested. If they are not interested, their data will be eliminated from this file. For cohorts 2-15, after the participant completes the final/third survey, her data will be eliminated from this file, if she chooses not to be contacted for future studies. If she chooses to be contacted for future studies, her information name and phone number (nothing else) will be kept and it will be recorded that she has completed participation, but is willing to be contacted in the future. Subsequently, each time she is contacted, this file will be updated to include a summary of the call. During each call, UIC staff will query the woman about her interest in being contacted in the future. If she chooses not to be contacted from future studies, her name and phone number will be eliminated from this contact log. If she chooses to be contacted for future studies, her name and phone number will remain in the contact log. Participants’ contact information will be kept until after participants decide to stop active participation or 5-7 years after the study is completed.

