
With regard to payment, participants will obtain \$80 in total throughout their participation in the trial. After Session 1, they will receive \$10. After Session 2, they will receive \$20. After Session 3, they will receive \$25. After they complete the 20-30 minute Survey 3, six months after participating in Session 3, they will receive \$25.

The materials for the workshops have been provided.

TRP 75 Latina Women	Compensation for Participants	Juan Diego 75 Latina Women
Three 2 Hour educational classes across 3 consecutive weeks	↔	Three 2 Hour educational classes across 3 consecutive weeks

Sessions will be held with 5-8 recruited participants		Sessions will be held with 5-8 recruited participants
These are 'closed' group format (once a woman is enrolled in a particular group, she cannot change to another group and has to complete all 3 sessions).		These are 'closed' group format (once a woman is enrolled in a particular group, she cannot change to another group and has to complete all 3 sessions).
At Session 1, Participants will complete: 1) Informed consent 2) Survey 1; 3) 1 ½ Hour Breast Cancer Education session;	\$10 Cash ↔	At Session 1, Participants will complete: 1) Informed consent 2) Survey 1 3) 1 ½ Hour Breast Cancer Education session;
At Session 2, Participants will complete: 1) 1 ½ Hour Interpersonal Communication workshop.	\$20 Cash ↔	At Session 2, Participants will complete: 1) 1 ½ Hour Diet Educational workshop.
At Session 3, Participants will complete: 1) 1 ½ Hour Volunteerism; workshop 2) Survey 2;	\$25 Cash ↔	At Session 3, Participants will complete: 1) 1 ½ Hour Physical Activity workshop; 2) Survey 2;
Booster Calls one month after Session 3. Every month thereafter for 6 months.		Booster Calls one month after Session 3. Every month thereafter for 6 months.
At 6 months post-participation, participants will complete: 20-30 minute Survey 3	\$25/Cash ↔	At 6 months post-participation, participants will complete: 20-30 minute Survey 3

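### Surveys 2 and 3 are tied to Session 3 in the detailed procedure, and no rule covers a woman who stops the workshops earlier but has not withdrawn from data collection

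*Combined protocol and SAP*

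**What the plan says.** **Survey 2.** Section 6.2 (Phase 3): "After the Session 3, participants will be asked to complete Survey 2 (T2) before leaving the site".

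**Survey 3, detailed text.** Section 6.2 (Phase 3): "Six months after participation in Session 3, participants will be asked to complete Survey 3, which will take about 20-30 minutes". The payment paragraph in the same section uses the same anchor: "After they complete the 20-30 minute Survey 3, six months after participating in Session 3".

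**Survey 3, looser text.** Section 3.0: "Our outcomes will be measured by Surveys assessed during Session 1, Session 3, and six months post-participation in workshops for 20-30 minutes". Section 6.4 repeats this. The schedule table in Section 6.2 has: "At 6 months post-participation, participants will complete: 20-30 minute Survey 3". Section 9.0 places the screening comparison six months after taking part in the interventions.

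**Attendance.** Groups are closed. Once enrolled, a woman is told that "she cannot change or switch to another group's session", and the schedule table expects her to complete all three sessions. Nothing says what follows if she does not.

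**Removal.** Section 5.1, in the Phase 3 list, gives participants the right to be removed from the research and adds: "This is a development study and therefore, no further information will be collected on the subject". Section 6.1 has the same sentence for the Phase 1 and 2 focus groups. The Phase 7 removal text in Section 5.1 leaves it out.

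**Missing data and other sources.** Section 9.0 plans multiple imputation. It also mentions a sensitivity analysis in women with complete medical record data, but no section describes how or when records are obtained.

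**The concern.** Take a woman who consents, completes Survey 1, attends Session 1 and then stops, without asking to leave the research. On the detailed wording she has no occasion for Survey 2 and no date from which Survey 3 is counted. Staff who follow that wording would not survey her, so stopping the programme turns into a missing outcome.

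This matters because attendance at Session 3 comes after allocation. The arms receive different workshops before Survey 2 on either account of the schedule: Sessions 2 and 3 in the table, Sessions 1 and 2 in Section 3.0. They also differ by site and by the community health workers who deliver the sessions. Attendance can therefore differ by arm for several reasons, and women who stop early may well differ in their readiness to be screened. If outcomes are sought only from women who reach Session 3, the Aim 1 and Aim 2 comparisons rest on a group selected after allocation. Outcomes that were never sought generally cannot be recovered in the analysis.

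**Working it through.** **1. The passages side by side.**

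| Place | What starts the clock | Covers a woman who misses Session 3? |
|---|---|---|
| Section 6.2, Survey 2 | End of Session 3, on site | No |
| Section 6.2, Survey 3 text | Participation in Session 3 | No |
| Section 6.2, payment text | Participation in Session 3 | No |
| Sections 3.0 and 6.4 | End of participation in workshops | Possibly; no date or procedure |
| Section 6.2, schedule table | End of participation | Possibly; no date or procedure |
| Section 9.0 | Taking part in the interventions | Possibly; no date or procedure |

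So the Survey 3 anchor is inconsistent, and even the looser version does not schedule her.

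**2. The plan's own counts.** Sections 3.0, 5.0 and 6.4 expect 240 women to enrol and 150 to complete. Non-completion is 240 − 150 = 90, and 90/240 = 37.5%. Section 9.0 counts 450 survey points for 150 women, and 450/150 = 3 surveys each. That is a set with no missed survey. The documents do not split the 90 into women who stop before Session 3 and women lost during the six months afterwards.

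**3. The stated detectable effect.** Section 9.0 gives OR = 2.8 for 150 women, two-sided 0.05, power 0.80. The education-arm screening rate is not stated. With 75 per arm and the pooled two-proportion formula, power for OR 2.8 is 0.81 if that rate is 20% and 0.80 if it is 60%, but 0.61 at 10% and 0.87 at 30%. The figure is consistent with the plan at some rates and cannot be confirmed. The present point does not depend on it.

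**4. How selection could act (all rates assumed; complete cases only).** Let true six-month screening be 35% in both arms, so the true OR is 1.0. Let women who stop before Session 3 screen at 15%, and let a fraction *f* stop. Among women with a Survey 3:

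observed rate = (0.35 − *f* × 0.15)/(1 − *f*)

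- *f* = 0.10: (0.35 − 0.015)/0.90 = 37.2%
- *f* = 0.25: (0.35 − 0.0375)/0.75 = 41.7%
- OR = (0.417/0.583)/(0.372/0.628) = 1.20, favouring the arm with more stopping

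Compared the other way round, the OR is 1/1.20 = 0.83. With equal stopping in both arms, or with stoppers who screen at 35% like the rest, it is 1.0.

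**5. How much the unmeasured women could matter (assumed 75 completers and 45 non-completers per arm).** Suppose completers screen at 20% and 41.2%, which is OR 2.8. If non-completers screen at 20% in both arms, the empowerment rate among all enrolled is (75 × 0.412 + 45 × 0.20)/120 = 33.2% against 20%. The OR is then (0.332/0.668)/(0.20/0.80) = 1.99. If every education and no empowerment non-completer were screened, the OR would be 0.35; the reverse gives 12.0. These are outer limits that treat all 90 as unmeasured. They are not estimates.

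**The case against.** **The looser wording may already include early stoppers.** No section makes attendance at Session 3 an explicit condition for Survey 3. This stands: a reader might infer that early stoppers are excluded by rule, and the documents do not say so. But the looser text gives no date or procedure for them, and the detailed text and payment text point the other way.

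**Removal is not the same as stopping.** A reader might infer that leaving the workshops triggers the Section 5.1 rule and ends all collection. It does not. The rule covers a woman who asks to be removed from the research, which is ordinary withdrawal. Two things remain. The development-study rationale is carried over from the focus-group phases and does not fit an efficacy comparison. And the protocol offers no recorded middle course. The consent pages were not available, so whether they offer one cannot be judged.

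**A contact procedure exists.** Section 6.2 provides a mailed letter after five unanswered calls or a non-working number, a returned-to-study status and contact by preference, none of it limited to Session 3 attenders. That is useful machinery, but it is for women who cannot be reached. It sets no survey date for a reachable woman who stopped attending.

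**Missing data are handled.** Multiple imputation is planned, and Section 12.1 prefers mixed models partly for their handling of missing data. So it would be wrong to say that the Aim 1 odds ratio must describe Session 3 attenders only; that assumes a complete-case analysis the plan does not state. Even so, imputation under missing at random would fill in early stoppers from women who stayed, and medical records have no collection procedure.

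**The numbers are hypothetical.** This is correct. The OR of 1.20 uses invented rates, and the 90 non-completers may mostly be lost after Session 3.

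**Conclusion.** The point holds as a gap in the procedure. Survey 2 depends on being at Session 3, the Survey 3 anchor is inconsistent, and no text schedules either survey for a woman who has a Survey 1 but misses Session 3. Stopping the programme and withdrawing from data collection are not distinguished. If staff follow the detailed wording, Aim 1 screening and the later Aim 2 measurements are missing by design for these women.

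The size and direction of any bias are unknown, because the number who stop before Session 3 is not given for either arm. The OR of 1.20 only shows that a null effect could be distorted under assumed rates in a complete-case analysis; it is not a finding about this trial. Nor do the documents label any outcome primary. Screening is the Aim 1 outcome.

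I rate this as a cheap improvement that should be made, not as a defect that invalidates the comparison.

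**What to change.** 1. In Section 3.0, Section 6.2 (Survey 2 text, Survey 3 text, payment text and schedule table) and Section 6.4, count Surveys 2 and 3 from the calendar date of the cohort's Session 3. Offer both to every woman who completed Survey 1, whatever her attendance, using the existing calls and letter. Make the time point in Section 9.0 agree.
2. For Phase 3, replace the development-study sentence in Section 5.1 with two recorded choices: stop sessions and/or booster calls but still be surveyed, or withdraw from all data collection. Record the number of sessions attended.
3. Apply this to cohorts still open. At least Cohort 1 had finished when this version was written, so for earlier cohorts report early stoppers by arm and state the analysis population.

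**Cost.** Protocol and consent wording, some extra calls to less engaged women, and a $25 Survey 3 payment for each early stopper who responds. If all 90 expected non-completers were early stoppers and all responded, that would be 90 × $25 = $2,250. The true figure should be lower.

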3.0 Objectives/Aims

The primary goal of this proposed work is to develop materials and conduct a trial that would examine the relative efficacy of education and empowerment interventions to improve breast cancer screening among Chicago-based Latinas. With regard to our objectives, we proposed to:

Aim 1: Develop and compare the efficacy of a breast health empowerment intervention on guideline-concordant screening compared to an education intervention, using an area-level treatment control group design with a community-based sample of 150 Latinas. The empowerment arm will include breast health and empowerment information (e.g., how to begin conversations, where to volunteer). The education arm will include only breast health information. Content draws from my team's existing materials. Hypothesis: Empowerment participants will have increased screening compared to education participants.

Aim 2: Compare interventions' effects on psychosocial facilitators of screening across six months. Hypothesis: Empowerment participants will have sustained increases in self-reported self-efficacy, norms, support, and knowledge about breast cancer screening compared to education participants.

Aim 3: Compare interventions' network effects through egocentric network analysis. Hypothesis: Empowerment participants will have greater social connectedness related to breast health and network size and will have referred a greater number of peers to participate in the study compared to education participants.

Aim 4: Characterize intervention effects on family and friends of intervention participants.

Aim 5: a) Determine the incremental costs for each additional woman screened for the empowerment approach relative to the education approach, combining new cost data with existing effect measures in our trial. Hypothesis: The empowerment intervention will have low incremental costs for each additional woman screened, especially when including indirect effects. b) Use those data and published literature to compare approaches in terms of achieving HP2020 goals and costs for additional life-years gained across 10 years, using existing simulation platforms. Hypothesis: The empowerment intervention will be more cost-effective than the education intervention in terms of life years gained.

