4.0 Eligibility

4.1a Inclusion criteria for target participants:

- Age 52-75 years old;
- Identification as Latina/Hispanic/Chicana female;
- Residence in Pilsen, Little Village, East Side or South Chicago;
- No history of health volunteerism;
- No history of breast cancer; and
- Lack of a mammogram within the last two years

4.1b Inclusion criteria for target interventionists:

- Age 52-75 years old;
- Identification as Latina/Hispanic/Chicana female;
- Residence in Pilsen, Little Village, East Side or South Chicago;
- A history of health volunteerism;

4.1c Inclusion criteria for Phase 4 participants:

- Age 18 years or older;
- No history of participating in Phase 3; and,
- Identification as family/friend of a Phase 3 participant

4.2 Exclusion criteria:

- Not meeting all inclusion criteria;
- Participation in Phase 1 or 2

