5.1 Recruitment

For Phase 3, we will recruit approximately 150 Latina women (75 at TRP and 75 at Juan Diego):

- Flyers will be posted at Centro Comunitario Juan Diego, The Resurrection Project and other community venues within target areas (Pilsen, Little Village, East Side and South Chicago,) and be distributed by electronic listservs in English and Spanish.
- Participants may also recruit their peers through sharing flyers/coupons and/or providing [name] contact information for screening. Participants will have the opportunity to take recruitment coupons throughout the three intervention sessions. They will be told that they can recruit other women until the third survey/they complete participation in the project. If they choose to take coupons, study staff will record which numbers belong to which participant via their participant id. The number of coupons given to each participant will depend on the participant's interest in distribution and how many they want. The study staff will record the total number each person obtains as well as the respective codes. When recruiting others, seed participants will provide individuals with coupons that have unique tracking codes. How many coupons are distributed and to whom will depend on the seed participants' interests and actions after they take the coupons from study staff. When interested individuals call, they will provide the unique tracking code on their coupon. After the call, the staff member will update the file that includes identifiable elements by inputting the coupon code. That said, no other information from the event will be kept in the database, including whether the individual agreed to be screened or ultimately participated.
- They will be compensated \$15 for each peer who contacts the study team, regardless of whether the peer is eligible and the extent to which they choose to undergo screening, consent, or participating in the intervention.
- Interested participants will call the PI, [name], or UIC staff [Appendix P], who will enter the name, address and phone number in a Call Log; screen women for eligibility; and obtain scheduling information.

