Referring peers will be identified once sessions/workshops are completed, based on the Call Log. They will be identified by a unique tracking code that each woman who calls will give, which will be on the coupon given to referring peers by study team staff. Peers will also be encouraged to recruit other women from their social networks to participate and will be compensated \$15 for their time and effort. When recruiting, they will provide individuals with coupons that have unique tracking codes, which will be linked to the seed. The purpose of the coupons is twofold. First, it will be used as a type of snowball sampling, wherein participants will be able to recruit their family and friends to participate in the study. To note, individuals who are recruited will not participate within the same cohort as the seed participant (who will have already started the program and be in a closed session). As well, the seed participant will not know/be told by study staff who contacted them nor who ultimately decided to participate. Second, the use of coupons will be a behavioral measure with regard to participants' interest in disseminating information related to the study (Aim 3 outcome). In this case, we will be measuring the number of participants who are interested in taking flyers and the number of individuals they reach via who contacts for screening. To note, at no point will the screening process of those recruited be connected with participants' names.

The 'seed' will have the opportunity to take flyers throughout the three intervention sessions. They will be told that they can recruit other women until the third survey/they complete participation in the project. The study staff will record the total number each person obtains as well as the respective codes. When recruiting others, seed participants will provide individuals with coupons that have unique tracking codes. How many coupons are distributed and to whom will depend on the seed participants' interests and actions after they take the coupons from study staff. When interested individuals call, they will provide the unique tracking code on their coupon. After the call, the staff member will update the file that includes identifiable elements by inputting the coupon code. That said, no other information from the event will be kept in the database, including whether the individual agreed to be screened or ultimately participated.

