9.0 Data Analysis Qualitative

For **Phase 1, 2, 4 and 7**, [name] and her team [Appendix P] will lead content analyses with inductive and deductive approaches[53, 54] in Atlas.ti.[55] She and two UIC students [TBA] will read transcripts and generate codes. We will compare notes, review data, cluster similar ideas into representative themes, and discuss areas of disagreement until consensus is reached. A final codebook will be used for re-analysis. Sample sizes are within the recommended range to meet thematic saturation.[53,54]

Quantitative

For **Phase 3**, our project will include 3 sets of analyses to examine the 3 outcomes – breast cancer screening, psychosocial facilitators (self-efficacy, norms, support, and knowledge), and social network dissemination. All analyses will be conducted in statistical packages (SPSS, SAS, R).

We will use multiple imputation techniques to handle missing data.⁶⁵ Measures will be assessed and included if they have adequate reliability (Cronbach's $\alpha \geq 0.70$). We will first conduct descriptive statistics. We will identify covariates based on theory and bivariate analyses to examine 1) intervention differences in demographic, healthcare, and pre-study factors (e.g., screening history) and 2) the relationship of these factors to each other and outcomes (e.g., screening). We will conduct a multivariable logistic regression to examine study arm differences in guideline-concordant screening six months after participating in interventions. We will conduct sensitivity analyses, using only women 1) with complete medical record data and 2) recruited by Study Site staff. Based on power analyses to estimate the minimal detectable effect of study arm differences among 150 Latinas on screening, $p < .05$, power = .80 and two-tailed tests, we would be able to detect a medium/large effect in a logistic regression (OR = 2.8).

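### Peer-referred women are kept out of the seed's cohort but not out of the other arm, so the education comparator can include women referred by an empowerment seed

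*Combined protocol and SAP*

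**What the plan says.** All references are to the combined protocol and SAP.

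- **Comparator.** Section 3.0, Aim 1: "The education arm will include only breast health information". The empowerment arm adds training in starting conversations and in volunteering.
- **Assignment.** Aim 1 is to be tested "using an area-level treatment control group design with a community-based sample of 150 Latinas". In section 6.2, empowerment sessions belong to one community organisation and education sessions to the other, so arm is site. Section 4.0 gives a single residence criterion for everyone: "Residence in Pilsen, Little Village, East Side or South Chicago".
- **Peer referral.** Sections 5.1 and 6.2 let participants in either arm take coupons and pay them for each peer who calls. Seeds are told that "they can recruit other women until the third survey/they complete participation in the project". On placement, section 6.2 says only that "individuals who are recruited will not participate within the same cohort as the seed participant".
- **Expected traffic.** Aim 3 predicts that empowerment participants "will have referred a greater number of peers to participate in the study compared to education participants". Section 6.4 sets up Phase 4 to study spill-over to family and friends.
- **Tracing.** Section 5.1: "When interested individuals call, they will provide the unique tracking code on their coupon". Sections 5.1 and 6.2 then state that nothing further about the call is kept, including whether the caller took part. Section 7.1 links the Call Log to consent forms only, not to questionnaires.
- **Analysis.** Section 9.0 fits a multivariable logistic regression of screening on study arm. It adds: "We will conduct sensitivity analyses, using only women 1) with complete medical record data and 2) recruited by Study Site staff". Clustering of peers referred by peers is raised only for the network outcomes.

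**The concern.** A cohort is not an arm. A woman referred by an empowerment seed can satisfy the cohort rule by joining an education cohort at the other site. The referral window runs to the six-month survey, so many referrals can come after the seed has been trained to talk to friends and family about breast health. The plan expects this outreach to work: it predicts more referrals from empowerment seeds and counts screening among family and friends as an indirect effect in Phase 5.

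If such women enter the education arm, that arm is no longer purely the comparator that Aim 1 describes, and part of the empowerment effect could appear on the wrong side of the comparison. The Aim 1 primary model has no term or rule for this.

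**Working it through.** **Step 1. Is there a barrier anywhere in the text?** Four places could supply one.

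| Place | What it restricts | Bars crossing arms? |
|---|---|---|
| 6.2, peer referral | Recruit and seed not in the same cohort | No |
| 4.0, residence | One of four areas, same list for both arms | No |
| 4.2, exclusions | Inclusion criteria not met; Phase 1 or 2 participation | No |
| 3.0, area-level design | Names the design; does not tie a caller's area to an arm | Not stated |

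No section says how a coupon caller is assigned to a site.

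**Step 2. The plan's own figure.** Section 9.0 gives a minimal detectable OR of 2.8 (150 women, two-sided 0.05, 80% power) without a control rate. With 75 per arm and a two-proportion normal approximation (pooled variance under the null):

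- p1 = 2.8·p0 / (1 − p0 + 2.8·p0), with p0 the education-arm rate.
- p0 = 0.20: p1 = 0.56/1.36 = 0.412, power 0.81.
- p0 = 0.60: p1 = 0.808, power 0.80.

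So 2.8 is consistent with a control rate near 20% or near 60%, and it is not shown to be wrong.

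**Step 3. One-way dilution (illustration).** Take 2.8 as the true OR. Let c be the share of education women reached by an empowerment seed and f the fraction of the effect they gain.

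- Diluted education rate = p0 + c·f·(p1 − p0).
- At p0 = 0.20 and c·f = 0.10: 0.20 + 0.10 × 0.212 = 0.221. The OR is (0.412/0.588)/(0.221/0.779) = 2.46.

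| c·f | OR, p0 = 0.20 | Power | OR, p0 = 0.30 | Power |
|---|---|---|---|---|
| 0 | 2.80 | 81% | 2.80 | 87% |
| 0.05 | 2.62 | 76% | 2.64 | 83% |
| 0.10 | 2.46 | 71% | 2.50 | 79% |

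A value of c·f = 0.05 means 5% of education women gaining the full effect, or 10% gaining half of it. The documents give none of p0, c or f.

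**Step 4. Same-arm referral works the other way.** Let p0 = 0.25, so p1 = 0.483. Suppose 30% of empowerment women were referred by empowerment seeds and gain an assumed further odds factor of 1.5 (OR 4.2, rate 0.583).

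- Empowerment rate = 0.483 + 0.30 × (0.583 − 0.483) = 0.513.
- With no cross-arm referral: OR = (0.513/0.487)/(0.25/0.75) = 3.16.
- With c·f = 0.10 as well, the education rate is 0.273 and the OR is 2.80 again.

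The net direction is therefore not fixed.

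**Step 5. Can the planned check be run?** The staff-recruited analysis needs each woman's recruitment source. Under section 6.2 the code a caller gives is logged, but not whether she took part. Section 11.0 keeps coupon numbers and call counts under the seed's record, in a file from which a woman is removed after her third survey unless she agrees to future contact. The Call Log may hold the code beside the caller's name, but section 7.1 does not let it be linked to questionnaires. As written, recruitment source appears not to reach the analysis file.

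**The case against.** The case against a strong version of this point is substantial.

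- **Direction.** A reader might infer that cross-arm referral must pull the OR toward 1. The documents do not support that. Step 4 shows an opposing force, and section 4.0 requires no mammogram in the last two years, so a friend whom the outreach got screened before enrolment is no longer eligible. This stands.
- **Mechanism.** A friend receives a conversation about breast health, and the education arm teaches breast health anyway. She does not receive the communication or volunteerism workshops, and coupons can be taken before the seed has completed them. Full transfer of the effect is therefore an upper bound. This stands.
- **Likelihood.** An area-level design with 75 women from each site makes crossing less likely. A reader might take the scheduling text in section 6.2 to mean that convenience decides the site. It says only that the organisations choose session dates to suit women already recruited. This stands, but less likely is not barred.
- **Existing check.** The staff-recruited analysis removes every peer referral, cross-arm ones included. It is a genuine check. It leaves the primary estimate unchanged, drops uncontaminated peer-referred women as well, and depends on data that step 5 could not trace.
- **Power.** The plan's 2.8 is a detectable effect, not an expected one. Leakage changes the contrast being estimated, not what 150 women can detect. This is why the figures in step 3 are illustrations.

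**Conclusion.** The gap holds. The plan as written permits women referred, and possibly coached, by an empowerment seed to be enrolled as education comparators, and the Aim 1 primary model does not address it. This can dilute the contrast. It is not shown that it will, and the net bias could go either way.

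The size is unknown. At an assumed 20% control rate, c·f of 0.05 to 0.10 costs about 5 to 10 points of power (81% to 76% or 71%). At 30% it costs about 4 to 8 (87% to 83% or 79%). These figures take 2.8 as the true OR, assume 75 analysed per arm, and ignore same-arm referral. A reader might carry the same model to 20% of education women gaining the full effect (OR 2.19, power 60% at a 20% control rate). Nothing in the documents supports leakage that large. Dilution of Aims 2 and 3 was not calculated and is not claimed.

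A second finding is firmer, because it rests on the text alone: the data rules in sections 6.2 and 7.1 need to be reconciled with the section 9.0 analyses that depend on recruitment source.

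**What to change.** 1. **Placement rule (sections 5.1 and 6.2).** Use the coupon code given at the call to identify the seed's site, and do not enrol the caller in the opposite arm. Offer a later cohort at the seed's site. If she cannot attend there, do not enrol her, but still pay the seed and count the call for Aim 3.
2. **One coded field (sections 6.2 and 7.1).** Amend the data rules so that referral source (staff, or peer with the seed's arm) is stored under the participant's study code, without the seed's identity. For women already enrolled, fill it in where still recoverable, before the coupon link is deleted under section 11.0.
3. **Analysis (section 9.0).** Report the number of cross-arm referrals and repeat the Aim 1 model without them. Keep the staff-recruited analysis, because same-arm referral remains and may push the OR upward.

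The cost is a short addition to the recruitment text, one field, one extra model and a small amendment to the data-retention wording. A few callers who could attend only the other site are lost. Same-arm referral is not removed. For cohorts already enrolled, only items 2 and 3 can apply.
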